### **Power Model Analysis**

```
proc mixed data = <data in> alpha = 0.05;
  by parcat1n parcat1 pkday fast paramn param;
  model lpk = ldose / cl residual ddfm = kr2;
  ods output solutionf = <data out>;
run;
```

### **Power Model Analysis (Between-subject Variability)**

```
proc mixed data = <data in> covtest alpha = 0.05;
  by parcat1n parcat1 pkday fast paramn param;
  class ldose;
  model lpk = ldose / cl residual ddfm = kr2;
  ods output covparms = <data out>;
run;
(Note: Pooled Geometric CV (%) = 100*(sqrt(exp(estimate)-1)))
```

### **Power Model Analysis (Lack of Fit Test)**

```
proc mixed data = <data in>;
  by parcat1n parcat1 pkday fast paramn param;
  class dose;
  model lpk = ldose dose / htype = 1 ddfm = kr2;
  ods output tests1 = <data out>;
run;
```

### **ANOVA Model Analysis**

```
proc mixed data = <data in> alpha = 0.05;
  by parcat1n parcat1 pkday fast paramn param;
  class dose;
  model ldnpk = dose / cl residual ddfm = kr2;
  lsmeans dose / cl pdiff;
  ods output lsmeans = <data out>;
  ods output diffs = <data out>;
  ods output tests3 = <data out>;
run;
```

## **8.6. Safety and Tolerability Assessments**

### **8.6.1. Adverse Events**

All AEs will be coded using the Medical Dictionary for Regulatory Activities (MedDRA) Version 24.0 (or higher if a new version is issued during the study; see the DMP for more details).

A treatment-emergent adverse event (TEAE) will be defined as an AE that starts during or after the first dose, or starts prior to the first dose and increases in severity after the first dose.

A treatment-related TEAE will be defined as a TEAE with a relationship of related to the study treatment, as determined by the investigator.

All AEs will be listed. In addition to the data recorded in the database, the listings will include derived onset time and duration. Onset time will be calculated from the time of the last associated dose for TEAEs only. Where the last associated dose is referring to the last dose received prior to the start of a TEAE.

The frequency of subjects with TEAEs and the number of TEAEs will be summarised for the following categories:

- TEAEs (overall, serious, leading to discontinuation, and leading to death) by treatment
- TEAEs by severity and treatment
- Treatment-related TEAEs (overall, serious, leading to discontinuation, and leading to death) by treatment
- Treatment-related TEAEs by severity and treatment

The frequency of subjects will be summarised separately for TEAEs and treatment-related TEAEs by the following:

- System organ class, preferred term, and treatment
- Preferred term and treatment

For the AE data the following rules will apply:

- For the derivation of treatment-emergent status (applicable to all AEs): If the start date/time of an AE is incomplete or missing, an AE will be assumed to not be a TEAE, unless the incomplete start date/time or the end date/time indicates an AE started after the first dose.
- For the derivation of treatment-related status (applicable to TEAEs only): If the study treatment relationship for a TEAE is missing, a TEAE will be assumed to not be a treatment-related TEAE.
- For the derivation of onset time (applicable to TEAEs only): If the start date/time of a TEAE is missing, onset time will not be calculated. If the start date/time of a TEAE is incomplete, where possible, the minimum possible onset time will be calculated and presented in ‘ $\geq$ DD:HH:MM’ format (eg, if the date/time of the last associated dose is 01MAY2019/08:00 and recorded start date/time of a TEAE is 03MAY2019, then the minimum possible onset time will be calculated by assuming a TEAE started at the first hour and minute of 03MAY2019 [03MAY2019/00:00], thus will be presented as onset time  $\geq$ 01:16:00 in the listing). If the start date of a TEAE is the same as the date of the last associated dose but the start time of a TEAE is missing, an onset time will be presented as ‘ $\geq$ 00:00:01’. Any clock changes will be accounted for in the derivation.

- For the derivation of duration (applicable to all AEs): If the end date/time of an AE is missing, duration will not be calculated. If the start or end date/time of an AE is incomplete, where possible, the maximum possible duration will be calculated and presented in ‘ $\leq$ DD:HH:MM’ format (eg, if the start of an AE date/time is 01MAY2019/08:00 and its recorded end date/time is 03MAY2019, then the maximum possible duration will be calculated by assuming an AE ended at the last hour and minute of 03MAY2019 [03MAY2019/23:59], thus will be presented as duration  $\leq$ 02:15:59 in the listing). Any clock changes will be accounted for in the derivation.
- For the calculation of TEAE summary statistics: If the severity of a TEAE is missing, that TEAE will be counted under the ‘missing’ category.
- For the calculation of TEAE summary statistics: If a subject experienced multiple TEAEs with the same preferred term for the same treatment, this will be counted as 1 TEAE for that treatment under the maximum severity recorded.

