t _{max} ^b (h)	1.25 (1.00-3.00)	1.25 (1.00-2.00)	2.00 (1.00-3.00)	1.50 (1.00-3.00)	2.00 (1.00-4.00)	2.00 (1.00-2.00)
t _{1/2} (h)	1.04 (37.2)	1.01 (16.6)	1.19 (31.5)	1.64 (113.0)	2.33 (56.5)	3.22 (20.0)
C _{min} (ng/mL)	NA	NC	NC	NC	NA	8.10 (28.9)
RA _{AUC0-τ}	NA	1.14 (15.5)	NA	1.13 (18.7)	NA	1.21 (17.6)
RA _{Cmax}	NA	1.22 (32.3)	NA	0.953 (46.7)	NA	1.09 (39.9)

Note: C_{min} values are NC because the minimum concentration in all profiles was 0, and geometric mean was not calculated.

^a Refers to a AUC₀₋₂₄ for Day 1.

^b Median (min-max) presented.

N = number of subjects; NA = not applicable; NC = not calculated; QD = once daily; RA = accumulation ratio.

To date, none of the subjects receiving single or repeat administration of NST-6179 have exceeded the PK stopping criteria. Following single administration of 1000 mg NST-6179 (Cohort A5), the highest individual systemic NST-6179 exposure represented 73.8% and 25.2% of the stopping criteria for C_{max} and AUC₀₋₂₄, respectively. Following repeat

administration of 1000 mg NST-6179 QD for 14 days (Cohort B3), the highest individual systemic NST-6179 exposure represented 88.2% and 34.1% of the PK stopping criteria, based on C_{max} and AUC_{0-24} , respectively.

Overall, PK across the dose range of 50 to 1000 mg was generally consistent, with median t_{max} between 1 to 2 hours postdose, estimates for $t_{1/2}$ in the range of 1 to 3 hours, and no evidence of accumulation following QD administration. From 50 to 1000 mg, AUC and C_{max} increased in a manner that was generally proportional (or slightly more than proportional) to the increase in dose; as dose increased by 20-fold, geometric mean C_{max} and $AUC_{0-\infty}$ increased by 24- to 26-fold, respectively.

1.6.1.2. *Clinical Safety*

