## **3. STUDY ENDPOINTS**

### **3.1. Primary Endpoints**

The primary safety endpoints for this study are as follows:

- incidence and severity of adverse events (AEs)
- incidence of laboratory abnormalities, based on haematology, clinical chemistry, coagulation, and urinalysis test results
- 12-lead ECG parameters
- vital signs measurements
- physical examinations.

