##### Groups A1 to A6

It is planned for each subject in Groups A1 to A6 to receive only a single dose of NST-6179 or placebo during the study. Doses will be administered in the fasted state in accordance with a randomisation schedule on the morning of Day 1.

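### SAP 8.6.1, read literally, leaves an adverse event dated on the first-dose date without a clock time, and with no recorded worsening after the dose, out of every AE summary table

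*SAP*

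**What the plan says.** SAP 8.6.1 defines a TEAE as an AE that begins during or after the first dose, or one that begins earlier and becomes more severe afterwards. For an incomplete or missing start, the AE is "assumed to not be a TEAE, unless the incomplete start date/time or the end date/time indicates an AE started after the first dose".

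The summaries in the same section are restricted to TEAEs: "The frequency of subjects with TEAEs and the number of TEAEs will be summarised for the following categories". The tables by system organ class and preferred term, and all treatment-related tables, are restricted in the same way. The listings contain every AE.

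The section also has a rule for displaying onset. "Onset time will be calculated from the time of the last associated dose for TEAEs only". For a TEAE whose start date "is the same as the date of the last associated dose but the start time of a TEAE is missing", onset is shown as ≥00:00:01, that is, at least one minute after that dose in the SAP's day:hour:minute format.

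AE incidence and severity head the primary endpoints in SAP 3.1. For Groups A1 to A6, SAP 4.1 plans one dose per subject: "Doses will be administered in the fasted state in accordance with a randomisation schedule on the morning of Day 1".

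**The concern.** A start on the first-dose date with no time is the commonest form of ambiguous start one would expect on a dosing day, and the default resolves it against the drug being involved. In Part A the first-dose date is the only dosing date, dosing is in the morning, and Protocol 1.6.1.1 puts half-life "in the range of 1 to 3 hours, and no evidence of accumulation following QD administration", with median peak time at 1 to 2 hours. The default therefore acts on the day when a drug effect is most plausible.

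The loss carries through. Treatment-related TEAEs are a subset of TEAEs, so an untimed dose-day event that the investigator judged related would also leave the treatment-related tables. At stake is whether the tables for a primary endpoint in a first-in-human study can undercount events that the listings show.

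**Working it through.** **1. The SAP's own date examples.** Dose 01 May 08:00, TEAE start 03 May with no time: earliest start is 03 May 00:00, which is 1 day 16 h after the dose, matching the SAP's ≥01:16:00. AE start 01 May 08:00, end 03 May with no time: latest end is 03 May 23:59, giving 2 days 15 h 59 min, matching ≤02:15:59. So the SAP already treats a partial date as an interval.

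**2. The same interval logic applied to TEAE status.** Take the earliest and latest possible start and cap the latest at the end date/time. Onset after the dose is indicated only if the earliest possible start is not before it. The 08:00 dose time is an assumption; the documents give only the morning.

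| Recorded start | Recorded end | Possible start | Status under 8.6.1 |
|---|---|---|---|
| Dose date, no time | none | 00:00 to 23:59 | ambiguous: not a TEAE |
| Dose date, no time | same day 20:00 | 00:00 to 20:00 | ambiguous: not a TEAE |
| Dose date, no time | 3 days later | 00:00 to 23:59 | ambiguous: not a TEAE |
| Dose date, no time | same day 07:00 | 00:00 to 07:00 | before the dose: not a TEAE |
| Next day, no time | any | wholly after the dose | TEAE |
| Missing | after the dose | either side | ambiguous: not a TEAE |

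An end date/time can only lower the latest possible start. It never raises the earliest, so that limb of the exception cannot bring an event in.

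**3. Against the onset rule.** The ≥00:00:01 display is derived only for events already classed as TEAEs, so it does not change status. In Part A the last associated dose is the first dose. Under the default, the display is left with little more than same-date events with a recorded worsening. In Part B it still works for events dated Day 2 onward, which are TEAEs by date alone.

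**4. How much of the dose date follows the dose.** Assuming dosing between 08:00 and 10:00: (24 − 8)/24 = 66.7% and (24 − 10)/24 = 58.3%. Five half-lives from Protocol Table 6: 5 × 0.844 = 4.22 h (50 mg) and 5 × 2.91 = 14.55 h (1000 mg), so an 08:00 dose gives 12:13 and 22:33 the same day. For 1000 mg, a 07:00 dose gives 21:33 and an 11:00 dose gives 01:33 next day.

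**5. Effect of one subject**, if the event was that subject's only TEAE:
- Part A active group: 1/6 = 16.7 points.
- Part B active group: 1/8 = 12.5 points.
- Pooled placebo as planned: Part A 1/(6 × 2) = 8.3 points; Part B 1/(4 × 2) = 12.5 points.

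In a preferred-term table the event need only be the subject's sole TEAE of that term. These swings have the same size in either direction.

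**6. Scale.** Protocol 1.6.1.2 reports 89 AEs in 31 of 70 subjects (44.3%), blinded, both parts together. One event is 1/89 = 1.1%. Removing one subject gives 30/70 = 42.9%, a change of 1.4 points. The documents do not say how many AEs were untimed on the first-dose date. If 0% to 3% were (an assumption with no anchor in the documents), 0 to 0.03 × 89 = 2.7 events would be affected.

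**The case against.** The strongest reply is that the SAP asks for dates that indicate onset after the dose, not dates that prove it. The strict reading leaves the end-date limb idle and the same-date onset rule almost idle in Part A. An author who shows same-date TEAEs as at least one minute after the dose may well have meant such events to count. That is a fair guess at intent, but the status rule does not say it, and a programmer following the text would exclude the event. It supports a clarification; it does not remove the need for one.

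Second, the trigger should be close to empty. Protocol 7.2.1 requires time of onset, subjects are resident from Day −1 and questioned at least daily, and data are verified against source. This stands and keeps the expected effect small. It does not defend the direction of a rule written for exactly these incomplete records.

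Third, the listings are complete, safety is descriptive (SAP 8.6.6), and the rule treats active and placebo alike. All of this stands.

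Four stronger readings are tempting and not supported:
- That all untimed first-dose-date events are lost. An event with a recorded worsening after the dose is still a TEAE.
- That the SAP contradicts itself. The onset rule has work to do in Part B, so the two rules are mismatched, not incompatible.
- That dose escalation is affected. The stopping criteria in Protocol 3.7 do not use TEAE status.
- That the rule on missing causality, "If the study treatment relationship for a TEAE is missing, a TEAE will be assumed to not be a treatment-related TEAE", is the same fault. Such an event stays in the overall TEAE tables, and the investigator's opinion on relationship must be documented (Protocol 7.2.1), so no change is asked for there.

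**Conclusion.** The point holds on the literal text. The default errs in the less cautious direction for a primary safety endpoint, and the onset rule does not rescue the event. It is worth correcting, but the expected effect on this study's results is small.

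The conclusion assumes that an event on the first-dose date without a time does not by itself indicate onset after the dose. The swings of 16.7 and 12.5 points are the effect of a single case with no other TEAE, not an estimate of bias; the number of cases is unknown and may be zero. Part B events dated Day 2 or later, and the listings, are unaffected.

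**What to change.** In SAP 8.6.1, reverse the default: an AE with an incomplete or missing start is a TEAE unless the available start or end date/time shows that it began before the first dose and it did not worsen afterwards. The end date/time then becomes useful, because an AE that ended before dosing is shown to be pre-dose.

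At minimum, add that an AE dated on the first-dose date with no clock time is a TEAE unless its end date/time is before the first dose. That brings the status rule into line with the ≥00:00:01 rule.

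The cost is one or two sentences and the matching derivation, with no new table. AEs are monitored from consent and screening runs from Day −28 to Day −2, so the full reversal may count a few pre-dose or undated screening events as TEAEs. The minimum version avoids most of that. The change should be made before unblinding for analysis, as SAP 1 requires of the SAP itself.

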10. APPENDICES

Appendix 1: Adverse Event Reporting

Definitions

An adverse event (AE) is any untoward medical occurrence in a patient or clinical investigation subject administered a pharmaceutical product, which does not necessarily have a causal relationship with this treatment. An AE can therefore be any unfavourable and/or unintended sign (including a clinically significant abnormal laboratory finding), symptom, or disease temporally associated with the use of a study treatment, whether or not related to the study treatment.

Assessment of Severity

The investigator will be asked to provide an assessment of the severity of the AE using the following categories:

- **Mild:** Usually transient and may require only minimal treatment or therapeutic intervention. The event does not generally interfere with usual activities of daily living.
- **Moderate:** Usually alleviated with additional specific therapeutic intervention. The event interferes with usual activities of daily living, causing discomfort but poses no significant or permanent risk of harm to the subject.
- **Severe:** Interrupts usual activities of daily living, or significantly affects clinical status, or may require intensive therapeutic intervention.

Relationship to Study Treatment

The investigator (or designee) will make a determination of the relationship of the AE to the study treatment using a 2-category or binary approach system according to the following guidelines:

- **Not Related:** The AE is definitely caused by the subject's clinical state or the study procedure/conditions.
- **Related:** The AE follows a reasonable temporal sequence from administration of the drug, abates upon discontinuation of the drug, follows a known or hypothesised cause-effect relationship, and (if appropriate) reappears when the drug is reintroduced.

Follow-up of Adverse Events

Every reasonable effort will be made to follow up with subjects who have AEs. Any subject who has an ongoing AE that is related to the investigational medicinal product (IMP) or study procedures at the follow-up visit will be followed up, where possible, until resolution or until the unresolved AE is judged by the investigator (or designee) to have stabilised. This will be completed at the investigator's (or designee's) discretion. Any subject who has an ongoing AE that is not related to the IMP or study procedures at the follow-up visit can be closed out as ongoing at the investigator's discretion.

Adverse Drug Reactions

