### **8.1.2. Calculation of the Summary Statistics**

For continuous data the following rules will be applied:

- Missing values will not be imputed, unless specifically stated otherwise.
- Unrounded data will be used in the calculation of summary statistics.
- If the number of subjects with valid observations (n) <3, summary statistics will not be calculated, with the exception of n, minimum, and maximum.

- In general, as discontinuation data are not associated with any scheduled timepoint, they will be excluded from all calculations of summary statistics and statistical analyses. Exceptions may be made where justified.

For categorical data the following rules will be applied:

- For ordered categorical data (eg, AE severity), all categories between the possible minimum and maximum categories will be included, even if  $n = 0$  for a given category.
- For non-ordered categorical data (eg, race), only those categories for which there is at least 1 subject represented will be included; unless specifically stated otherwise.
- Missing values will not be imputed, unless specifically stated otherwise. A ‘missing’ category will be included for any parameter for which information is missing. This will ensure that the population size totals are consistent across different parameters.

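### SAP 8.6.1 treats a TEAE with no recorded causality as not treatment-related: any missing attribution can only lower the treatment-related totals, and no table described in the SAP would show it

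*SAP*

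**What the plan says.** SAP 8.6.1 defines the flag from the investigator's assessment: "A treatment-related TEAE will be defined as a TEAE with a relationship of related to the study treatment, as determined by the investigator". Among its rules for AE data it then covers the blank case: "If the study treatment relationship for a TEAE is missing, a TEAE will be assumed to not be a treatment-related TEAE".

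Three bullets later, missing severity is handled differently: "If the severity of a TEAE is missing, that TEAE will be counted under the" 'missing' category. That matches the default for categorical data in SAP 8.1.2, under which values are not imputed and a 'missing' "category will be included for any parameter for which information is missing". The default applies unless the SAP specifically says otherwise.

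The protocol (Appendix 1, Relationship to Study Treatment) has causality assessed "using a 2-category or binary approach system". It defines Not Related as: "The AE is definitely caused by the subject's clinical state or the study procedure/conditions".

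The flag feeds four groups of summaries in SAP 8.6.1. The first is "Treatment-related TEAEs (overall, serious, leading to discontinuation, and leading to death) by treatment"; the others are by severity, by system organ class and preferred term, and by preferred term alone. Each mirrors an all-causality summary, so half of the eight planned AE summaries depend on the flag.

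**The concern.** A blank causality field means that the investigator has not recorded a judgement. The rule gives it the same result as a recorded judgement of not related. On a two-category scale, leaving an event out of related in effect places it in the other category, and the protocol reserves that category for events whose other cause is definite. A blank field does not support that.

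The direction is also one-sided. In a first-in-human study with safety as its primary objective, the assumed value is the favourable one. The two AE attributes that the investigator judges, severity and causality, are treated differently when missing, without explanation. At stake is whether a reader of the treatment-related tables can tell a group with no related events from a group with an unattributed one.

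**Working it through.** The plan states no figure to reproduce, so the check is of the logic, followed by simple arithmetic.

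**Direction.** Let k be the number of TEAEs with missing relationship, and j (0 ≤ j ≤ k) the number of those that the investigator would have called related. Let R be the related-event count with complete attribution.

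- Reported count under the SAP rule = R − j, which never exceeds R.
- SAP 8.6.1 counts repeated TEAEs with the same preferred term in one subject once, at maximum severity. After that step the loss is at most j and still never a gain. In the by-severity table, a subject could move to a lower severity if the more severe of two such events is the unattributed one.
- The number of subjects with a related TEAE falls only for subjects who have no other related TEAE.

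**Size per subject.** Active group sizes come from SAP 4.1 (6) and 4.2 (8). The planned placebo subjects number 2 per group, pooled within each part (SAP Tables 1 and 2): 6 × 2 = 12 in Part A and 4 × 2 = 8 in Part B.

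| Group | Change in incidence for one affected subject |
|---|---|
| Part A active | 1/6 = 16.7 points (for example 0/6 reported in place of 1/6) |
| Part B active | 1/8 = 12.5 points (0/8 in place of 1/8) |
| Part A pooled placebo | 1/12 = 8.3 points |
| Part B pooled placebo | 1/8 = 12.5 points |

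**Illustration over an assumed missing rate.** Protocol 1.6.1.2 reports 89 AEs, of which 54 were considered not related, leaving 89 − 54 = 35 (39%). These are blinded interim data with active and placebo combined, and treating all 35 as related assumes that no attribution was missing. The missing rate m is an assumption, because the documents give none.

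| m | Related count, missing at random: 35(1 − m) | Related count, all missing would be related: 35 − 89m | Chance that at least 1 of 35 is affected: 1 − (1 − m)^35 |
|---|---|---|---|
| 0 | 35 | 35 | 0 |
| 1% | 34.7 | 34.1 | 30% |
| 2% | 34.3 | 33.2 | 51% |
| 5% | 33.3 | 30.6 | 83% |
| 10% | 31.5 | 26.1 | 97% |

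Across the whole study the loss is small at low rates. In a table for 6 or 8 subjects a single event is visible.

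**What stays in place.** The rule does not touch treatment-emergent status, so an unattributed TEAE remains in every all-causality summary. All AEs are listed with the data recorded, so the blank shows in the listing. None of the summaries described in SAP 8.6.1 has a row or footnote for missing relationship. The shells for tables, figures and listings are a separate document and were not available.

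**The case against.** The strongest reply is that the rule follows from the definition: a treatment-related TEAE is one that the investigator called related, and a blank field does not meet that. The protocol's Related category also asks for positive findings, such as a reasonable temporal sequence, so a blank supports neither category. Severity is a breakdown within a table, where an extra row is natural; relatedness selects which events enter a table. All of this stands as an explanation of the rule. It does not explain why the number of unattributed events goes unreported.

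Missing causality may also never occur. Protocol 7.2.1 asks for the investigator's opinion on relationship, and Appendix 5 requires queries to be resolved and the eCRF to be signed by the investigator. SAP 8.1.1 does list incomplete data entry and unanswered queries as pandemic risks, so missing data are foreseen in general, but nothing points to causality in particular. This stands: the effect may be zero.

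Four stronger readings are tempting, and the documents do not support them:

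- *The rule contradicts SAP 8.1.2.* It does not; that section allows specific exceptions, and this is one.
- *The event disappears from the report.* It stays in all the all-causality tables and in the listing.
- *SAP Section 10 should have declared it.* Protocol 8.4 has no rule for missing causality, so there was no departure to declare.
- *The active-placebo comparison is biased in the drug's favour.* The rule applies to both arms, so the direction of any effect on the comparison is not fixed.

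The primary AE endpoint is also incidence and severity of AEs, not of related AEs. Safety reporting is descriptive, and dose escalation rests on review during the study rather than on these final tables.

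**Conclusion.** The point holds as a cheap improvement to the reporting of treatment-related TEAEs. The rule is a permitted but unexplained exception. It differs from the handling of missing severity and fits poorly with the protocol's meaning of Not Related. When it applies, the related totals can only be too low, by 16.7 points (Part A) or 12.5 points (Part B) in an active group for one affected subject with no other related TEAE.

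This rests on two assumptions: that at least one attribution is missing at database lock, and that the investigator would have called that event related. If either fails, the effect is zero. The SAP was written against protocol Version 4, whereas the protocol reviewed here is Version 5; the Version 4 to 5 change summary lists no change to the causality definitions, so they are taken to be the same.

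A neighbouring rule ("If the start date/time of an AE is incomplete or missing, an AE will be assumed to not be a TEAE, unless the incomplete" or end date/time shows otherwise) also tends to remove events from the TEAE counts. It is a separate matter and does not alter this conclusion.

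**What to change.** Replace the missing-relationship bullet in SAP 8.6.1. The preferred wording would say that TEAEs with missing relationship are shown in a separate missing-relationship row or category, by treatment, in the treatment-related summaries. This imputes nothing and matches both the severity rule and the 8.1.2 default.

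The alternative is to count them as treatment-related and footnote their number. That is itself an imputation, in the conservative direction, and may slightly raise the related counts in both arms; the footnote lets the reader reverse it.

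Either version costs one sentence in the SAP, one line in the derivation, and a row or footnote in the affected tables. If no attribution is missing, the numbers do not change. The change should be made before unblinding, the point by which SAP Section 1 requires the plan to be final. A query on any blank causality field before database lock would make the rule less likely to be needed.

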A total of 70 subjects have been exposed to either NST-6179 or matched placebo in single doses up to 1000 mg and as multiple doses up to 1000 mg QD for 14 days. The study is ongoing and remains blinded, but analysis of the adverse events (AEs) has been performed as part of dose escalation reviews. A total of 89 AEs were reported in 31 subjects during the study period, the majority of which were mild (77 of the 89 AEs) and considered not related to NST-6179 treatment (54 of the 89 AEs). There were no severe or serious AEs reported during the study period. The most common AE (greater than 2 subjects) considered to be related to NST-6179 treatment was headache; 15 AEs reported by 7 subjects. There were no clinically significant changes or abnormalities in laboratory parameters, vital signs, ECG parameters, or physical examinations recorded at for any of the doses of NST-6179 administered. In summary, NST-6179 appears to be safe and well tolerated at single doses up to 1000 mg and repeated doses of 1000 mg QD for up to 14 days.

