## 4.2. Part B

Part B will comprise a double-blind, multiple-ascending dose, sequential-group study design. Overall, 40 subjects will be studied in 4 groups (Groups B1 to B4), with each group consisting of 10 subjects. Part B may start in parallel with Part A provided the exposure is not predicted to exceed an exposure shown to be safe and well tolerated in Part A.

Potential subjects will be screened to assess their eligibility to enter the study within 28 days prior to the first dose administration. Each subject will participate in 1 treatment period only and reside at the study site from Day -1 until the morning of Day 16.

All subjects will return for a follow-up visit 10 to 14 days after their final dose.

Based on the ongoing review of the safety, tolerability, and PK results, additional non-residential visits may be required. The number of additional visits per subject will not exceed 3 per period and will not extend beyond 28 days after each final dosing occasion.

[figure not shown]
In each of Groups B1 to B4, 8 subjects will receive NST-6179 and 2 subjects will receive placebo. For all subjects, dosing is planned to be once daily (QD) on Days 1 to 14, inclusive. However, dosing frequency and duration in Part B may be changed following review of data from groups in Part A or earlier groups in Part B. The dose regimen will comprise no less than once every 2 days and will not exceed 4-times-daily dosing. The dosing duration will comprise no fewer than 7 consecutive days and will not exceed 28 consecutive days of dosing. There will be a minimum of 14 days between dose escalations for each group in Part B. The total daily dose administered will not be predicted to exceed an exposure shown to be safe and well tolerated in Part A.

Up to 3 further groups of 10 subjects (8 active:2 placebo) may be included in Part B.

An overview of the study design is shown in [Figure 3](#), and the planned dose levels are presented in [Figure 4](#).

The total planned duration of study participation for each subject (from screening through follow-up visit) is anticipated to be approximately 8 weeks.

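### The SAP plans a count of TEAEs, but its counting rule merges repeats of a term within a subject, so cells labelled as event counts would hold subject-by-term pairs

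*SAP*

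**What the plan says.** SAP Section 8.6.1 plans two kinds of adverse event table.

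- The first kind has two statistics: "The frequency of subjects with TEAEs and the number of TEAEs will be summarised for the following categories". The categories are TEAEs overall (with serious, discontinuation and death rows), TEAEs by severity, and the same two for treatment-related TEAEs.
- The second kind, by system organ class and preferred term and by preferred term alone, gives subjects only: "The frequency of subjects will be summarised separately for TEAEs and treatment-related TEAEs by the following".

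The section closes with rules for handling the data. The last one is introduced as applying to the calculation of TEAE summary statistics. It says that where a subject had "multiple TEAEs with the same preferred term for the same treatment, this will be counted as 1 TEAE for that treatment", the single TEAE is placed "under the maximum severity recorded".

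The qualifier about the same treatment has to be read with the design. For Part B the SAP says: "Each subject will participate in 1 treatment period only and reside at the study site". Section 4.1 gives Part A subjects one treatment period as well.

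**The concern.** The rule changes what is being counted. A table that promises a number of TEAEs should count events. Under the rule, a subject with several headaches adds one to that cell, as does a subject with a single headache. The result is neither an event count nor a subject count, and it will not reconcile with the AE listing, which shows every event.

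In the severity tables the milder repeats disappear and only the worst remains, so the distribution of events by severity changes too.

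The incidence and severity of adverse events is the first primary endpoint in SAP Section 3.1. No other event-level AE summary is planned. If these cells do not count events, recurrence can be seen only by reading the listings.

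**Working it through.** **1. Scope of the rule.** The question is whether it can be confined to subject counts as it stands.

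- It says what is counted as one TEAE, not how a subject is counted.
- Its introduction refers to TEAE summary statistics without restriction. The bullet before it, on missing severity, opens the same way and is also framed per TEAE.
- Its maximum-severity clause can act only in tables split by severity. Among the planned tables these are the two severity summaries, and both carry the number of TEAEs. The system organ class and preferred-term tables have no severity split.
- Neither the SAP nor the protocol gives a separate rule for event counts.
- With one treatment per subject, the same-treatment qualifier excludes nothing. In Part B the merge runs over the planned 14 dosing days and follow-up.

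**2. Small worked example (invented data).** Subject 1 has headache three times (mild, mild, moderate) and nausea once (mild). Subject 2 has headache once (mild).

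| Basis | Total | Mild | Moderate |
|---|---|---|---|
| Every event | 5 | 4 | 1 |
| Rule as written | 3 | 2 | 1 |
| Subjects | 2 | | |

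The 3 is the number of subject-by-term pairs.

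**3. Illustration from the protocol.** Inputs from Protocol Section 1.6.1.2 (blinded, pooled, AEs not restricted to TEAEs): 89 AEs in 31 subjects, 77 mild, none severe, 54 judged not related, and "headache; 15 AEs reported by 7 subjects". The documents state no figure under the SAP rule, so there is none to reproduce first.

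Assume that the 15 headaches are treatment-emergent, share one preferred term and were all judged related, and that nothing else merges.

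- Headaches removed: 15 − 7 = 8, which is 8/15 = 53% of them.
- All events: 89 − 8 = 81, a fall of 8/89 = 9.0%.
- Related events: 89 − 54 = 35, then 35 − 8 = 27, a fall of 8/35 = 22.9%.

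Merging of any other repeated term would lower 81 and 27 further, so under these assumptions both are upper limits.

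The protocol sentence does not state outright that all 15 headaches were judged related. If some were not, headache alone could remove anywhere from 0 to 8 related events, leaving 27 to 35. The fall from 89 to 81 does not depend on this.

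**4. Severity split.** With no severe AEs, 89 − 77 = 12 are moderate. The severities of the headaches are not given, so only a range can be stated.

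| Case | Mild | Moderate | Mild share |
|---|---|---|---|
| Every event | 77 | 12 | 77/89 = 86.5% |
| All 8 removed are mild | 69 | 12 | 69/81 = 85.2% |
| All 8 removed are moderate | 77 | 4 | 77/81 = 95.1% |

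The last row is extreme. It needs at least 9 of the 12 moderate AEs to be headaches, for example one subject with 9 moderate headaches and six subjects with one each (9 + 6 = 15). The mild share can therefore move in either direction.

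**The case against.** The strongest reply is that the rule is a stated, reproducible definition: the SAP plans a number of TEAEs and then says what counts as one. On that view the problem is only a label. Relabelling would indeed be a valid remedy, but as the text stands a reader will take the cell for a count of events, and it is not one.

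Second, the SAP refers to separate table shells for detail, and these were not available. They may define the event column as a raw count. A programmer might also read the rule as a subject-level convention, since taking the maximum severity is usual there. Both are possible, and they are the reason for not asserting that the final tables will be wrong. But the SAP does not defer to the shells on this point. If they count every event, they contradict its text.

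Third, the consequences are limited. Subject-level incidence, the preferred-term tables, worst severity per subject and term, and the listings all stand. Safety analysis is descriptive, and active groups have only 6 or 8 subjects, so recurrence can be read from the listings. Only cells in which a subject repeats a term change; the serious, discontinuation and death rows are unlikely to. All of this stands and limits the weight of the point.

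Fourth, counting every record could overstate episodes if a change in severity opens a new record. Protocol Section 7.2.1 and Appendix 1 do not say whether it does. That is worth settling, but it is no reason to merge separate episodes.

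**Conclusion.** The concern holds. As written, SAP Section 8.6.1 promises a number of TEAEs and prescribes a rule that yields subject-by-preferred-term pairs wherever a term recurs in a subject. Recurrence is real in this study, as the headache data show.

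The percentages illustrate possible size. They rest on the assumptions listed with the calculation and come from interim data pooled over parts and treatments, so they will not appear in any planned table and do not measure distortion in a dose group.

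This should be corrected. It does not threaten the subject-level safety conclusions. Confidence is medium because the shells may already state a different convention.

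**What to change.** In SAP Section 8.6.1, limit the last rule to subject frequencies: a subject is counted once per preferred term, at the maximum severity. Add that the number of TEAEs counts every recorded TEAE at its own severity. State there, or in the data management plan, whether a change in severity within one continuous event creates a new record. Bring the table shells into line. If the pair count is what is wanted, keep the rule and relabel the cells as subject-by-preferred-term counts.

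The cost is a sentence or two and a check of the shells, with no new data. The SAP requires itself to be final before unblinding. If that point has passed, state the counting convention in the clinical study report as a deviation from the SAP.
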